#### **Background Information**

Minimally invasive colorectal surgery has dramatically improved postoperative outcomes, resulting in significantly shorter length of stay, pain, and overall cost.  Despite the advances in multimodal analgesia and enhanced-recovery pathways, the optimal strategy for perioperative analgesia has not yet been defined, and there may be a role for expanded use of regional anesthesia in minimally invasive surgery.

Regional anesthesia, specifically the transversus abdominis plane (TAP) block, has been shown to reduce postoperative pain and opioid requirements even in the context of minimally invasive surgery.  Surgeon-performed, laparoscopically placed TAP blocks are equivalent, or perhaps superior, to ultrasound-guided TAP blocks. Long-acting local anesthetics, specifically liposomal bupivacaine, have been shown to prolong the effect of TAP blocks over non-liposomal bupivacaine, and has also suggested a reduced length of stay and less overall cost, despite the high cost of the formulation. These findings suggest improved outcomes can be expected if a longer block can be achieved.

Liposomal bupivacaine is not currently available in Canada and is very costly. In addition, recent evidence has called into question the efficacy of liposomal bupivacaine, specifically regarding rebound pain. Rebound pain can occur with any type of regional anesthesia, but intravenous corticosteroids seem to mitigate this problem.

We hypothesize that addition of dexamethasone to bupivacaine can prolong the duration of sensory block to be similar to that achieved with liposomal bupivacaine, but at a much lower cost. Dexamethasone was chosen due to its current widespread use in regional anesthesia, long biological half-life (36-54 hours), low cost, availability, and absence of any evidence of harm with single-dose use.

Regional anesthetic supplemented with perineural dexamethasone, a potent corticosteroid, has shown improved efficacy and prolonged duration of anesthetic in a variety of regional anesthetic techniques as well as in spinal anesthesia.  The duration of sensory block can be nearly doubled when dexamethasone is combined with long-acting local anesthetics for perineural anesthesia in brachial plexus and interscalene blocks. 

Dexamethasone in combination with local anesthetic has been the subject of several meta-analyses and systemic reviews, which universally suggest a synergistic effect on duration of sensory block. . It remains unclear whether the effect is greater with systemic or perineural administration, with moderate quality evidence suggesting a stronger effect from perineural administration.

The adjunctive analgesic effect of dexamethasone is thought to be mediated by attenuating the release of inflammatory mediators, reducing ectopic neuronal discharge, and inhibiting potassium channel-mediated discharge of nociceptive C-fibres. Corticosteroids possess potent anti-inflammatory effects. Dexamethasone as an adjunct to local anesthetic is thought to work through reduction in inflammatory mediators, less ectopic neuronal discharge, and reduced potassium channel-mediated transmission in nociceptive C-fibres. Local vasoconstriction may also play a role. However, the exact mechanism by which dexamethasone reduces pain remains unknown. It also remains unclear whether the proven analgesic benefits are due to local (perineural) or systemic effects. While controversial, the burden of evidence points to increased effect from perineural administration. 

Local (incisional) subcutaneous injection of dexamethasone may also provide analgesic benefit. In a placebo-controlled randomized trial assessing subcutaneous injection of 16mg dexamethasone into cesearean-section incisions against intravenous administration of the same dose and a placebo group, local injection was found to have significantly less postoperative pain than the other two groups. In addition, the local injection group had less postoperative nausea than the placebo group, suggesting a protective effect against postoperative nausea and vomiting.

There are no known safety concerns about single-dose perioperative dexamethasone, and no reports of harm could be identified with its use as an adjunct to regional anesthesia. Three studies have reported on potential harms with administration for brachial plexus block; no prolonged nerve palsies were identified in 407 patients.  One study reported a minor, but clinically insignificant, rise in blood glucose concentration. A 2018 Cochrane review examined adverse side effects of dexamethasone in surgical patients and concluded that there was no effect on surgical site infection, unclear effects on wound healing, and a transient (<12 hour) mild rise in blood glucose concentration of uncertain significance. The effect was similar for low (4-5mg), moderate (8-10mg) or high (12-20mg) doses. Notably, this review assessed effects of intravenous dexamethasone, which would be expected to have more pronounced systemic effect than perineural injection.

Although widely used in clinical practice, adjunctive application for regional anesthesia is an off-label use. Dexamethasone has not been approved for perineural administration by Health Canada, the United States Food and Drug Administration, nor any other regulatory body.

### **Trial Objectives and Purpose**

The objective of this trial is to investigate the effect of adjuvant dexamethasone in combination with bupivacaine to increase the depth and duration of sensory block in laparoscopically placed transversus-abdominis plane (TAP) blocks. The primary outcome will be total opioid consumption, in hydromorphone equivalents, in the first 48 hours after surgery. Secondary outcomes will be length of stay in the post-anesthetic care unit (PACU) and length of stay in hospital. The results of this study will serve as a proof-of-concept and will guide future research exploring adjuvant dexamethasone use in TAP blocks, specifically optimal dosing and ultimately a head-to-head comparison with systemic dexamethasone.

The results of this study will be of benefit to patients presenting for colorectal surgery, and more likely any type of abdominal surgery. Further research and refinement of regional anesthesia protocols adds to the armamentarium of anesthetic modalities available to anesthesiologists and surgeons and may offer a strategy for improved patient care.

#### **Trial Design**

This study will be carried out as a prospective, randomized, single-blinded clinical trial.

The intervention group will receive intraoperative laparoscopically assisted, surgeon-placed TAP blocks using 1mL/kg of 0.25% bupivacaine with epinephrine 1:200,000 combined with 16mg dexamethasone divided into 4 aliquots to be placed at two locations per side along the anterior axillary line between the

costal margin and the iliac crest. The control group will have TAP blocks with the same dose of bupivacaine without dexamethasone. The blocks will be performed at the conclusion of surgery. Postoperatively, all patients will be provided with patient-controlled analgesia (PCA) with institutional standardized orders.

Intravenous dexamethasone will not be given for prevention of postoperative nausea and vomiting (PONV); prophylaxis of postoperative nausea and vomiting will be at the discretion of the anesthesiologist, but can include any of ondansetron, haloperidol, or dimenhydrinate. If PONV occurs and is refractory to non-corticosteroid treatment, dexamethasone may be given for treatment but would result in exclusion from the trial. General anesthetic technique will be at the discretion of the anesthesiologist, but the following adjunct anesthetic drugs will not be permitted, due to independent effects on postoperative pain: dexmedetomidine, lidocaine, and ketamine. These adjuncts are occasionally used in anesthetic protocols, but their exclusion will not affect the quality of the anesthetic provided, and their use is not considered standard of care. All patients will be provided with a standardized hydromorphone-based patient-controlled analgesia (PCA) for a minimum of 48 hours postoperatively.

The primary outcome will be total opioid consumption, in hydromorphone equivalents, in the first 48 hours after surgery. Secondary outcomes will be length of stay in the post-anesthetic care unit (PACU), length of stay in hospital, and total opioids administered in the PACU.

A computer-generated random number table will be used to randomize patients to receive either bupivacaine alone (n=60) or bupivacaine plus dexamethasone (n=60). Allocation will be performed in a 1:1 ratio. Group allocation will be concealed via a centralized third-party research assistant. Group allocation will be blinded to study participants, study investigators, post-anesthetic care unit (PACU) nursing staff, and surgical ward nursing staff. The attending surgeon and attending anesthesiologist on the day of surgery will not be blinded to the intervention, however, they will be asked to conceal the anesthetic modality from the PACU staff and ward nurses. The intervention will be charted in the Operating Room record, but not on the anesthetic record. PACU nurses commonly review the anesthetic record, whereby they would discover the intervention.

A blinded, centralized, third-party research assistant or study investigators will carry out data collection. Postoperative opioid consumption will be quantified through chart review as well as assessment of patient-controlled analgesia (PCA) usage at 24 and 48 hours following the operation. Recording the doses of opioids administered in the medication administration record (MAR) is standard practice by PACU nursing staff at the study institution. PCA pumps automatically document cumulative opioids administered and can easily be checked at the bedside, as well as being recorded in the MAR. Length of stay in hospital is readily available from the chart.

Followup for primary and secondary outcomes will be limited to 48 hours postoperatively, and assessment of infiltration sites for complications will be performed at 6 weeks postoperatively.

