Both groups will receive surgeon-placed, laparoscopically visualized transversus abdominus plane (TAP) block at the end of the surgical procedure prior to emergence from anesthesia as an analgesic adjunct using 1mL/kg of 0.25% bupivacaine with epinephrine 1:200,000 divided in four aliquots to be placed at two locations per side along the anterior axillary line between the costal margin and the iliac crest. The intervention group will have dexamethasone 16mg combined with the bupivacaine / epinephrine, with 4mg to be injected at each TAP site, for a total of 8mg dexamethasone per side. The study drug will be provided from wardstock available in the operating room, and will be prepared by nursing staff as per standard perioperative nursing practice. The control group will have TAP blocks with the same dose of bupivacaine without dexamethasone. The bupivacaine / lidocaine solution will be sourced from the hospital pharmacy, and is purchased from Sandoz Canada

Currently, the colorectal surgeons based at Royal University Hospital are experienced with performance of TAP blocks and have been performing them for several years. If there is interest from other general surgeons in participating in the trial, in-person training will be provided to that surgeon by one of the experience surgeons to ensure standardization of the technique.

Following surgery, patients will be extubated fully awake in the operating room and transferred to the PACU. In PACU, both groups will have access to nurse-administered multimodal analgesia including rescue hydromorphone for postoperative pain relief. Standard antiemetics will be available as well. Upon discharge from PACU, hydromorphone-based patient-controlled analgesia (PCA) will be initiated and continued for a minimum of 48 hours postoperatively. Morphine-based PCA can be substituted if there is a contraindication to hydromorphone. Both groups will receive acetaminophen 975mg PO Q6H scheduled for 48 hours then PRN.

Surgical ward nurses will be not informed that the patient is involved in the study, as participation is not relevant to postoperative care, which will be administered as per usual. The study institution maintains a standardized colorectal-surgery postoperative pathway directing advancement of diet, intravenous maintenance fluids, deep-vein thrombosis prophylaxis, and urinary catheter management.

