#### **Statistics**

Primary Outcome:

Total opioid consumption at 24 and 48 hours will be gathered from the PCA record and Medication Administration Record (MAR). Intention to treat analysis will be performed. Parametric data will be analyzed with the students t-test for statistical significance.

Secondary Outcome: Opioid consumption in the PACU will be reported in hydromorphone equivalents and compared with chi square test. Length of stay in PACU and length of stay in hospital will be reported as a mean +/- standard deviation (SD), along with confidence intervals and compared with chi square test.

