#### **Quality Control and Quality Assurance Procedures**

Patients will be monitored intraoperatively by a qualified staff anesthesiologist. Following surgery, patients will be extubated fully awake in the operating room and transferred to the PACU with supplemental oxygen. In PACU patients will be monitored by dedicated nursing staff and will have access to nurse-administered analgesia. Standard antiemetics will be available as well, and dexamethasone can be given systemically as a rescue antiemetic. If this occurs, the patient will be excluded from the study. Following discharge from PACU, patients will be monitored on the ward by nursing staff and postoperative care will be administered as per usual protocol.

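### The protocol promises intention to treat but excludes randomised, treated patients who receive systemic dexamethasone for PONV, so the primary analysis set contradicts itself

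*Protocol*

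**What the plan says.** - **Analysis principle.** Protocol, Statistics, under the primary outcome: "Intention to treat analysis will be performed". No exception is attached.
- **Exclusion rule, first statement.** Protocol, Trial Design: "If PONV occurs and is refractory to non-corticosteroid treatment", then "dexamethasone may be given for treatment but would result in exclusion from the trial".
- **Exclusion rule, second statement.** Protocol, Quality Control and Quality Assurance Procedures, in the text on recovery-room care: "dexamethasone can be given systemically as a rescue antiemetic. If this occurs, the patient will be excluded from the study". Here the trigger is rescue use in general; Trial Design limits it to refractory PONV.
- **Timing.** Trial Design: "The blocks will be performed at the conclusion of surgery". Treatment of subjects places the block "at the end of the surgical procedure prior to emergence from anesthesia".
- **Outcome data.** Trial Design and Statistics take opioid doses from the PCA record and the medication administration record (MAR), with PCA use assessed at 24 and 48 hours.
- **Related rule.** Selection and withdrawal of subjects says that data already gathered on a participant who withdraws during data collection are destroyed. It does not say that this applies to patients excluded for rescue dexamethasone.

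**The concern.** Intention to treat means that everyone randomised is analysed in the assigned arm. A rule that removes some of them for what happens after treatment defeats it. The rule is stated in two sections, so it does not look like a slip of wording.

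Rescue for PONV is not a baseline characteristic. It follows randomisation, and the study drug may change how often it occurs. The protocol's own background gives a reason to think so: in a trial of incisional injection at caesarean section, "the local injection group had less postoperative nausea than the placebo group". That is one trial in another operation and by another route, so it is a pointer and not an estimate. If control patients are rescued more often, the patients left in each arm are no longer comparable, and the comparison of 48-hour opioid use is biased to the extent that rescued patients differ from the rest in opioid use.

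An unresolved analysis set also leaves the choice open until outcomes have been seen. That could be as early as the analysis at 50% recruitment, which can stop the trial for superiority of either arm.

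**Working it through.** **1. Can the statements be reconciled as written?**

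- Statistics: analyse all randomised patients as assigned.
- Trial Design and Quality Control: patients given systemic dexamethasone for PONV leave the trial or study.
- Treatment of subjects: the block precedes emergence, so PONV treated afterwards arises in a patient who is already randomised and treated.
- No passage limits the exclusion to trial conduct, and none defines a modified intention-to-treat or per-protocol set.

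An analyst cannot satisfy all of these. This step needs no arithmetic and carries the finding.

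**2. How much could exclusion matter?**

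Inputs from the protocol: 60 per arm (Trial Design); alpha 0.05 and effect size 0.8 (Selection and withdrawal of subjects), the latter read as SD units. Inputs not in the protocol, and so assumed: the proportion *p* excluded in each arm, and the distance δ, in SD, of excluded patients from the mean of their full arm.

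Shift of the retained-arm mean = −[p/(1−p)] × δ. The bias is the difference in shift between arms. Rejection is from the noncentral *t* with the retained numbers, two-sided 5%, no true effect.

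Worked case, 15% v 5%, δ = 1: 0.15/0.85 − 0.05/0.95 = 0.1765 − 0.0526 = 0.124 SD, with 51 and 57 patients retained.

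| Excluded, control v dexamethasone | Retained | δ (SD) | Bias (SD) | Rejection favouring control + dexamethasone* | Total |
|---|---|---|---|---|---|
| 5% v 5% | 57/57 | any | 0 | 2.5 + 2.5% | 5.0% |
| 5% v 2% | 57/59 | 0.5 | 0.016 | 3.05 + 2.04% | 5.1% |
| 5% v 2% | 57/59 | 1 | 0.032 | 3.69 + 1.65% | 5.3% |
| 10% v 3% | 54/58 | 0.5 | 0.040 | 4.0 + 1.5% | 5.5% |
| 10% v 3% | 54/58 | 1 | 0.080 | 6.18 + 0.86% | 7.05% |
| 15% v 5% | 51/57 | 0.5 | 0.062 | 5.03 + 1.14% | 6.2% |
| 15% v 5% | 51/57 | 1 | 0.124 | 9.29 + 0.47% | 9.8% |
| 20% v 5% (extreme) | 48/57 | 1 | 0.197 | 16.81 + 0.15% | 17.0% |

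*If rescued patients use more opioid than their arm mean. If they use less, the two components swap.

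Leaving out the extreme row, the unequal cases give a bias of 0.016/0.8 = 2% to 0.124/0.8 = 15% of the planned effect.

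**3. Power at a true effect of 0.8, bias running against dexamethasone**

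- No exclusions, 60 per arm: 99.1%.
- 5% v 2%, δ = 0.5: 98.7%.
- 10% v 3%, δ = 1: 96.5%.
- 15% v 5%, δ = 1: 93.5%.
- Extreme case: 86.2%.

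**4. Cross-checks**

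- A model in which a normal PONV liability correlates 0.3 to 0.5 with opioid use gives 0.018 to 0.083 SD and 5.1% to 7.1% over 5% v 2% to 15% v 5%.
- Simulation of 20,000 trials gives a bias of 0.016 SD and 3.2% + 2.0% at the low end, and 0.122 SD and 9.2% + 0.5% for 15% v 5% at 1 SD.
- If δ is measured from the retained patients instead, the shift is p × δ. For 15% v 5% at 1 SD the bias is 0.15 − 0.05 = 0.10 SD, with 8.1% rejection by normal approximation.

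**5. What does keeping rescued patients cost?**

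Suppose rescue gives a control patient the full 0.8 SD effect (an assumption). The contrast becomes 0.8 × (1 − 0.05) = 0.76 SD at 5% control rescue, power 98.5%, and 0.8 × (1 − 0.15) = 0.68 SD at 15%, power about 96%, with 60 per arm.

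**The case against.** **The Statistics section governs.** On this reading the analysis keeps everyone, and exclusion elsewhere describes conduct only; details of the analysis set may sit in an analysis plan that is not shown. The reading is possible, but the protocol does not state it, and the wording about exclusion from the study leans against it. A separate plan might choose a set, but the two protocol statements would still conflict.

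**The size is assumed.** This stands. There is no rescue rate, no arm difference for this block and no link between rescue and opioid use. The Trial Design trigger is narrow, so 15% or 20% control-arm rescue has no anchor in the document. Equal exclusion gives no bias. In one of the two directions the bias works against dexamethasone, and false claims of benefit become rarer, not commoner.

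**Keeping rescued patients dilutes the contrast.** This also stands. At 15% control rescue the loss is 0.80 − 0.68 = 0.12 SD, about the same as the 0.124 SD bias from exclusion in the 15% v 5%, 1 SD case. A proof-of-concept trial might reasonably want a contrast free of systemic dexamethasone. But dilution does not raise false rejection when there is no effect, whereas unequal exclusion can, and intention to treat is the principle the protocol itself chose.

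**The withdrawal rule is a different matter.** Agreed. It concerns voluntary withdrawal, its consent terms are not shown, and it is secondary here. Adverse events have their own reporting routes, so their loss is not claimed.

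**Conclusion.** The concern holds and should be fixed before the primary analysis set is put to use. The textual conflict is certain: unqualified intention to treat and a twice-stated exclusion of randomised, treated patients cannot both be applied.

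The consequence is less certain. Over the assumed range 5% v 2% to 15% v 5%, about 3 v 1 to 9 v 3 patients of 60, the bias is roughly 0.02 to 0.12 SD and rejection under no effect is 5.1% to 9.8%. These figures depend on assumed rescue rates and on an assumed difference in opioid use. The low end is negligible, and the documents do not determine the direction. The harm is mainly possible bias: power at 0.8 stays at 93.5% or more outside the extreme case. The bias is avoidable, because rescued patients' opioid doses are in records the trial already uses.

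**What to change.** 1. In Trial Design and in Quality Control, separate being off protocol from being out of the analysis, so that both agree with Statistics. The two descriptions of the trigger (refractory PONV, and rescue use in general) should also be reconciled.
2. State that every randomised patient is included in the primary analysis in the assigned arm, using 48-hour opioid data from the PCA record and MAR whether or not rescue dexamethasone was given.
3. Report rescue dexamethasone use by arm. Present the analysis without rescued patients as a sensitivity analysis only.
4. Secondary: amend the withdrawal text so that data collected up to withdrawal are kept and analysed as far as consent and the ethics board allow.

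Items 1 to 3 cost protocol wording and no new data collection. Item 4 depends on consent and ethics terms that are not shown. The statistical price is the dilution shown in the working, which 60 per arm can absorb at the stated effect size. Rescue treatment and clinical care are left as they are.

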Subjects will be free to withdraw voluntarily from the study at any point. The process for withdrawal can be initiated by the participant at any time by informing any of the study staff of the decision to withdraw. No explanation for withdrawal will be sought. If this occurs prior to randomization, no patient information will be collected for study purposes, and the patient will still be eligible to undergo surgery as planned without compromise to care. If withdrawal occurs during data collection, data collected on the subject will be destroyed, and they will continue receiving post-operative care as per standards. Either of the attending anesthesiologist or attending surgeon caring for the patient on the day of surgery has the ultimate discretion as to whether a patient is included or excluded from the study. If the attending surgeon or anesthesiologist deems the patient unfit to participate in the study, this will be communicated to the study coordinator, and the patient will be withdrawn. All adverse events and protocol deviations will be reported to the study coordinator, study investigators, and appropriate Research Ethics Board. Subjects who are withdrawn from the study due to the occurrence of an adverse event will be followed up by one of the study's physician investigators while in hospital. If the adverse event is believed to have been related to the study drug, a detailed note will be made in the patient's medical record and passed on to future care providers. Subjects withdrawn from the study due to an adverse event will not be replaced. Any adverse events will result in unblinding by notification of the principle investigator.

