#### **Treatment of subjects**

All study subjects will be assessed by an anesthesiologist in the Preoperative Assessment Clinic (PAC) prior to their scheduled procedure date. At this time, subjects will undergo a comprehensive medical assessment, including a review of their current prescription medications. At the discretion of the reviewing

anesthesiologist, subjects will be counselled regarding which medications may be safely continued or held prior to their procedure.

All subjects will receive standard anesthetic, analgesic, amnestic, and anxiolytic medications under the care of a qualified anesthesiologist. Vasopressors will be used when appropriate as part of standard practice in the operating room. The choice of anesthetic technique will be at the discretion of the treating anesthesiologist, however the anesthetic adjuncts of dexmedetomidine, lidocaine, and ketamine will not be permitted due to significant potential for confounding due to independent effect on postoperative pain.

All patients will be premedicated with acetaminophen 975 mg on the day of their scheduled procedure in the Same Day Surgery (SDS) unit prior to arriving in the operating room. Once in the operating room, standard monitors including noninvasive blood pressure, electrocardiography, pulse oximetry, and capnography will be applied as per Canadian Anesthesiologists' Society (CAS) guidelines. Neither group will receive systemic dexamethasone for PONV prophylaxis; alternative PONV prophylaxis may include ondansetron or haloperidol, to be given at the discretion of the treating anesthesiologist.

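### The anesthesiologist and surgeon know the arm, at a time the protocol does not fix, while they control co-treatment and exclusion; late, limited disclosure would close this cheaply

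*Protocol*

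**What the plan says.** **Who knows the arm.** The Trial Design section states: "The attending surgeon and attending anesthesiologist on the day of surgery will not be blinded to the intervention". Others are blinded: "Group allocation will be blinded to study participants, study investigators, post-anesthetic care unit (PACU) nursing staff, and surgical ward nursing staff". The two physicians are asked to keep the arm from PACU and ward nurses, and the intervention is charted in the operating room record but not in the anesthetic record. The protocol gives neither the time of randomization nor the time at which the operating-room team learns the arm.

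**Who chooses co-treatment.** Under Treatment of subjects: "The choice of anesthetic technique will be at the discretion of the treating anesthesiologist". Trial Design says the same, with limits: "General anesthetic technique will be at the discretion of the anesthesiologist, but the following adjunct anesthetic drugs will not be permitted". The barred adjuncts are dexmedetomidine, lidocaine and ketamine, and prophylactic intravenous dexamethasone is also ruled out. Other antiemetic prophylaxis is left to the anesthesiologist. No rule is given for intraoperative opioid.

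**When and by whom the block is given.** Trial Design: "The blocks will be performed at the conclusion of surgery". Treatment of subjects adds: "Both groups will receive surgeon-placed, laparoscopically visualized transversus abdominus plane (TAP) block at the end of the surgical procedure prior to emergence from anesthesia". The study drug comes from operating-room stock and "will be prepared by nursing staff as per standard perioperative nursing practice".

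**Who may exclude.** Under Selection and withdrawal of subjects, either the attending anesthesiologist or the attending surgeon "has the ultimate discretion as to whether a patient is included or excluded from the study". A patient whom one of them deems unfit is withdrawn. Separately, rescue systemic dexamethasone for refractory nausea leads to exclusion (Trial Design; Quality Control and Quality Assurance Procedures).

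**The concern.** The primary outcome is opioid use in the first 48 hours after surgery. Intraoperative opioid is not counted in it but can carry over into PACU and early PCA use. The protocol bars three adjuncts because of their own effect on postoperative pain, so it accepts that intraoperative drug choice can confound the outcome. It nevertheless leaves opioid, the drug class of the primary outcome, to a clinician who may know the arm.

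Two routes to bias are open:

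- **Co-treatment.** An anesthesiologist who knows that a patient will not get dexamethasone may give more opioid or antiemetic before emergence.
- **Exclusion.** Either physician may remove a patient on the day of surgery, and nothing requires that decision to be made before the arm is known. Removing randomized patients with the arm known would weaken the intention-to-treat comparison announced under Statistics. Central concealment protects the assignment, but not decisions taken after disclosure.

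The first route is avoidable, because none of the tasks described requires the anesthesiologist to know the arm.

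**Working it through.** **1. Does any task need the arm to be known?**

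| Task | Done by | When | Needs the arm? |
|---|---|---|---|
| Choice of anesthetic and antiemetic | Anesthesiologist | Before and during surgery | No |
| Decision to include or exclude | Anesthesiologist or surgeon | Day of surgery | No |
| Preparation of the block solution | Nursing staff | Not stated; must precede the block | Yes |
| Placement of the block | Surgeon | End of surgery, before emergence | No stated reason |

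Only preparation requires the arm. Both tasks that could carry bias can be finished without it.

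**2. Direction of the co-treatment route.** Extra intraoperative opioid in controls is outside the outcome and would lower their PACU and early PCA use. The observed difference in favour of dexamethasone would shrink. The main risk on this route is therefore lost power.

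**3. Size, as an illustration.** The inputs are:

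- 60 per arm (Trial Design).
- Alpha 0.05 and effect size 0.8 (Selection and withdrawal of subjects). The protocol does not state sidedness; two-sided is assumed here.
- Student's t-test (Statistics).
- Shifts of 0.1 and 0.2 SD, and an alternative true effect of 0.5 SD. These are assumptions. The protocol gives no SD, no intraoperative opioid figure and no carry-over figure.

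The protocol's sample size does not follow from its own inputs. With d = 0.8, two-sided 0.05 and the printed power of 0.08 read as 0.80, a t-test needs 26 per arm, or 52 in total, against the stated 120. That is a separate matter. The figures below use the stated 60 per arm.

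The formula is the noncentral t with df = 2 × 60 − 2 = 118, critical value 1.980 and noncentrality (d − shift) × √(60/2).

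| True effect d | Shift toward null | Net effect | Noncentrality | Power |
|---|---|---|---|---|
| 0.8 | 0 | 0.8 | 4.382 | 99.1% |
| 0.8 | 0.1 | 0.7 | 3.834 | 96.7% |
| 0.8 | 0.2 | 0.6 | 3.286 | 90.3% |
| 0.5 | 0 | 0.5 | 2.739 | 77.5% |
| 0.5 | 0.2 | 0.3 | 1.643 | 37.1% |

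**4. False positives under the same mechanism.** With no true effect and a shift that favours control, the chance of a false claim for dexamethasone falls from 2.5% to 0.6% (0.1 SD) or 0.1% (0.2 SD). The total two-sided rejection rate does rise, to 8.4% or 19.2%, but almost all of it (7.8% or 19.1%) lies in the tail that favours control.

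**5. Exclusion.** The protocol gives no expected number of exclusions and no link to outcome, so no size can be computed. The direction depends on who is removed and from which arm.

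**The case against.** The case against has real weight.

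- **Declared choice.** The trial calls itself single-blinded, so nothing is contradicted. This stands: the point is a design weakness, not an error.
- **Safeguards.** The outcome is largely patient-driven and pump-recorded. Patients, nurses and data collectors are blinded, PCA orders are standardized, and acetaminophen is scheduled in both arms. These measures reduce the risk. None of them limits what the anesthesiologist gives before emergence, or whom either physician excludes.
- **Disclosure time.** If the arm is revealed only when the block is drawn up, most of the anesthetic has already been chosen blind and the co-treatment route is small. This also stands, but the protocol does not secure it.
- **Assumed bias.** The shifts have no source in the document. They show what a shift would do, not that one occurs.
- **Imperfect fix.** The drug is prepared in the operating room and charted in its record, so the anesthesiologist may see it. This limits the gain, but the early disclosure is still removed.

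A reader might make two stronger inferences. The first is that unblinding inflates false positives in favour of dexamethasone; the mechanism described points the other way. The second is that arm-aware conversions to open surgery and exclusions undo the randomized comparison. The text does not support that: open surgery appears only as an eligibility criterion, no rule for conversion after randomization is given, and the clause on unfit patients does not say that the decision follows disclosure.

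**Conclusion.** The concern holds as a weakness in trial conduct that should be corrected. The protocol permits arm-aware co-treatment and arm-aware exclusion because it unblinds both physicians, fixes no time of disclosure and sets no end to their discretion. It does not show that either occurs.

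The size of any bias is unknown. On the co-treatment route the likelier harm is masking. That harm is modest if the true effect is the protocol's 0.8 SD, where power stays at 90.3% or more for shifts up to 0.2 SD. It is serious if the true effect is nearer an assumed 0.5 SD, where a 0.2 SD shift roughly halves the power. These figures rest on 60 analysed per arm, a two-sided t-test at 0.05, approximately normal data and assumed shifts. Exclusion could bias in either direction.

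**What to change.** In Trial Design, state that:

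- the central allocation is opened only when the block is about to be drawn up, after inclusion, including laparoscopic completion, is confirmed as final;
- the arm is disclosed only to the nurse who prepares the solution, and to the surgeon if needed;
- the arm is not disclosed to the anesthesiologist except by emergency code break.

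In Selection and withdrawal of subjects, state that the physicians' discretion to exclude a patient from the study ends once the allocation is opened. This concerns study membership only. Clinical care and the participant's own right to withdraw do not change.

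The cost is protocol wording and a short step at the end of each case, using the central third party already planned, with no extra staff. Blinding of the anesthesiologist may stay imperfect because the drug is prepared in the same room. Coded syringes prepared elsewhere would be stronger but would need further resources, and the point does not depend on them.
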